## 4. Study Design

### 4.1 Overview

Patients presenting to the emergency department who fulfill entry criteria will be asked to participate. A screening log will be kept listing all patients considered with reasons for patients not entering the study. Any patient whose information is reviewed in consideration for the study, even if not actually approached, is to be included in the screening log. The screening log will differentiate between those who are prescreened, i.e., who are reviewed but never progress to request for consent, from those who are screened, i.e., who are approached for consent, whether or not they actually sign consent or eventually participate in the study. Qualifying patients, once they have signed consent, will be stratified by age ( $\geq$  vs <age 18) and randomized 60:40 to RHB-102 or matching placebo. All patients will undergo laboratory testing and ECG, as specified below, once they have signed consent. However, only results of the pregnancy test (for women of childbearing potential) and a finger stick blood glucose (for patients with type 2 diabetes mellitus controlled by diet or oral medications) are required prior to treatment.

Patients will be started on oral fluids  $\geq$ 30 minutes after taking study medication (second dose for patients who receive 2 doses in ED) if they have not vomited during that period. Intravenous hydration should not be administered unless the patient has vomited or is clearly unable, after a reasonable period of time has elapsed since administration of study medication, to tolerate oral fluids.

At  $4\pm0.25$  hours after initial dosing, all patients are to have a repeat 12-lead ECG. Once stable, but not less than 4 hours after initial dosing, patients may be discharged from the emergency department. If a patient leaves the ED less than 4 hours after dosing, an ECG should be obtained if at all possible, even if the patient is leaving against protocol requirements.

On discharge, patients will be given an additional 3 doses of study medication to take at 24-hour intervals if nausea persists. Patients will be contacted daily for 4 days after discharge to determine their condition. Those patients who have persistent, worsening or recurrent nausea and/or vomiting during the follow-up period may be asked to come in for follow-up assessment by study personnel.

### 4.2 Study Drug Administration

After results of the pregnancy test and/or blood glucose (when required) are obtained and determined to be negative/within acceptable limits and the patient is randomized, the investigator or a designate will administer the first dose of study medication under observation. If the patient vomits within 15 minutes, regardless of whether pill fragments are seen, a second dose of study medication will be administered by the investigator or a designate. If a patient retches but does not actually vomit any gastric contents, no second dose will be administered. If a patient vomits again, regardless of how long after the second dose of study medication, no further study medication will be administered.

Patients vomiting  $\geq$ 30 minutes after the first dose of study medication may receive rescue antiemetics, either parenterally or orally. In addition, patients with

severe nausea  $\geq$ 30 minutes after dosing with study medication and which in the investigator's opinion requires treatment may receive rescue medication. Metoclopramide 0.3 mg/kg, maximum dose 10 mg, administered intravenously will be the default rescue medication. Oral metoclopramide or other antiemetics administered either intravenously or orally may be used at the investigator's discretion. **However, patients are not to receive ondansetron or other 5-HT3 antagonists by any route for at least 24 hours after administration of study medication either in the ED or after discharge.** The following 5-HT3 antagonists are available in the US: alosetron (Lotronex), dolasetron (Anzemet), granisetron (Sancuso and others), ondansetron (Zofran, Zuplenz and others), palonsetron (Aloxi).

Oral fluids will be administered as tolerated once a patient has not vomited for 30 minutes after dosing with study medication (second dose for those patients receiving 2 doses in the ED). Only patients who do not tolerate oral fluids after an adequate attempt at oral hydration may receive parenteral hydration. Patients are not to receive intravenous hydration until it is clear to the treating physician that the patient is clearly in need of parenteral hydration.

Patients tolerating oral fluids will be discharged once deemed stable by the attending physician but not prior to 4 hours after dosing and repeat ECG.

Patients who do not tolerate oral fluids will receive parenteral hydration.

Patients who are admitted but have not vomited or received antiemetics other than study medication may, at the investigator's discretion, continue treatment with study medication.

#### 4.3 Randomization and Blinding

As noted above, patients will be stratified by age and randomized 60:40 to receive either RHB-102 or matching placebo. Medication will be provided in kits of 5 pills: one for initial administration, one if repeat dosing is required in the emergency department (and which will be retained by the investigator if not required), and three which the patient will take home.

#### 4.4 Concomitant Therapy

If deemed necessary by the investigator, patients may take rescue antiemetics, either orally or intravenously, as described in section 4.2, above. Also, if deemed necessary by the investigator, patients may receive parenteral hydration. However, every effort should be made to avoid both rescue medications and parenteral hydration, and to proceed with oral hydration, unless it is clear that the patient will not be able to tolerate oral hydration.

**From the time a patient takes any antiemetic other than study medication, whether while in or after leaving the emergency department, or receives parenteral hydration, he or she will be deemed a treatment failure, even in the absence of vomiting.**

Patients may take antipyretic and antidiarrheal medication as needed prior to or after initial dosing with study medication. Patients may also take medications for gastrointestinal symptoms as long as they are not specifically antiemetics. For

example, they may use proton pump inhibitors or antacids. Once vomiting is controlled, patients should resume any medications they routinely take.

Patients for whom an intravenous medication (other than antiemetic) is indicated once on study may receive that medication in up to 100 mL fluid. This will not be considered parenteral *hydration*. For example, if a patient has a urinalysis suggesting infection and the investigator or other physician wish to give the patient an intravenous antibiotic dose, that will not be considered treatment failure as long as the drug is given in ≤100 mL fluid.

If once on study, a patient requires a medication which may prolong the QTc interval, he or she should not receive further study medication. However, evaluation of the patient should continue per protocol.

#### 4.4.1 Oral hydration guidelines

The following are guidelines for oral rehydration. These are suggested but not required; investigators may follow institutional procedures and should use clinical judgment in determining when and how much oral fluid to administer.

1. After ingestion of the study drug along with small amount of fluids, nothing else by mouth for the first 30 minutes.
2. At approximately 30 minutes after study drug administration, gently encourage drinking of approximately 8 ounces (240 mL) of fluid over the next 30 minutes.
3. At approximately 60 minutes after study drug administration, further encourage oral hydration according to patient symptoms, as follows:
  - a. The overall goal is for the patient to ingest approximately one liter over 1-2 hours after study drug administration. One liter is common, although as much as 2 liters may be taken, depending on the patient's volume status and symptom of nausea.
  - b. Alternatively, a patient may ingest 600-700 mL, indicate feeling better and want to be discharged. If, based on improvement in symptoms, the investigator feels confident the patient will do well at home, the discharge takes place.

Please note the following:

- Too much fluid given too quickly may increase symptoms of nausea.
- Too little fluid: in the absence of at least some ED rehydration, it is difficult to be confident the patient will further tolerate reasonable amounts of fluid at home (or to determine if the patient is failing hydration in the ED).

**From the time a patient takes any antiemetic other than study medication, whether while in or after leaving the emergency department, or receives any parenteral hydration, he or she will be deemed a treatment failure.**

#### 4.4.2 Serotonin syndrome

5-HT3 antagonists, including ondansetron, have been associated with serotonin syndrome. When given as a single agent, ondansetron overdose has been associated with serotonin syndrome. However, most reports of serotonin syndrome have been associated with concomitant use of serotonergic drugs (e.g., selective serotonin reuptake inhibitors (SSRIs), serotonin and norepinephrine reuptake inhibitors (SNRIs), monoamine oxidase inhibitors, mirtazapine, fentanyl, lithium, tramadol, and intravenous methylene blue). Some of the reported cases were fatal.

Symptoms associated with serotonin syndrome may include the following combination of signs and symptoms: mental status changes (e.g., agitation, hallucinations, delirium, and coma), autonomic instability (e.g., tachycardia, labile blood pressure, dizziness, diaphoresis, flushing, hyperthermia), neuromuscular symptoms (e.g., tremor, rigidity, myoclonus, hyperreflexia, incoordination), seizures, with or without gastrointestinal symptoms (e.g., nausea, vomiting, diarrhea). Patients should be warned about and monitored for the emergence of serotonin syndrome, especially with concomitant use of other serotonergic drugs. If symptoms of serotonin syndrome occur, discontinue RHB-102 and initiate supportive treatment.

All medications taken in the 7 days prior to study entry and from the time the patient arrives in the emergency room until he or she completes the study will be recorded in the case report form (CRF).

#### 4.5 Duration of Treatment

On discharge, patients who have not had further vomiting and have not required rescue medication in the emergency department will be given 3 additional doses of study medication to take once daily if necessary. Patients will be instructed to take additional study medication if they are nauseated (whether persistent or recurrent) or have any vomiting. However, patients are not to take study medication more than 3 days after study entry. Thus, if a patient receives an initial dose of study medication in the emergency department, feels well the next day and does not take study medication, but subsequently has a recurrence of symptoms, that patient may not take the remaining dose of study medication on day 5. Rather, the patient should return for reassessment during the follow-up period.

Patients or their caregivers are to complete a diary each day for 4 days, recording episodes of vomiting, diarrhea, presence and severity of nausea, presence/development of other signs or symptoms related to the gastroenteritis, and occurrence of adverse events. This diary may be completed either on paper or through a web-based system. Alternatively, patients or their caregivers will be contacted daily for up to 4 days following study initiation (until symptoms have resolved) to ascertain whether the patient had further vomiting, other sequelae of the acute gastroenteritis or required further medical care for the gastroenteritis. If symptoms persist for 3 days after study entry, the patient will be instructed to return for further evaluation on the third or fourth day.

For patients discharged prior to 8:00 pm, the ED day diary page is to be completed. The ED day diary page is to include only information regarding events after discharge from the ED; information on events during the patient's ED stay is not to be repeated in the diary. For those discharged 8:00 pm to midnight, or later, diary information is to be recorded only on the follow-up diaries. But vomiting episodes and adverse events occurring between 8:00 pm and midnight the preceding day should be included in the information captured.

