	
Any patient receiving rescue medication or parenteral hydration will be deemed a treatment failure.
 
Metoclopramide 0.3 mg/kg, maximum dose 10 mg, administered intravenously will be the default rescue medication. Oral metoclopramide or other antiemetics administered either intravenously or orally may be used at the investigator's discretion. However, patients are not to receive ondansetron or other 5-HT3 antagonists by any route for at least 24 hours after administration of study medication. The following 5-HT3 antagonists are available in the US: alosetron (Lotronex), dolasetron (Anzemet), granisetron (Sancuso and others), ondansetron (Zofran, Zuplenz and others), palonsetron (Aloxi).
 
Oral fluids will be administered as tolerated once a patient has not vomited for 30 minutes after dosing with study medication (second dose for those patients receiving 2 doses in the ED). Guidelines for administration of oral fluids are shown on page 20, section 4.4.1, of the protocol.
 
Patients tolerating oral fluids will be discharged once deemed stable by the attending physician but not prior to 4 hours after dosing. On discharge, patients will be given 3 additional doses of study medication to take once daily if necessary.
 
Patients who do not tolerate oral fluids may receive parenteral hydration. Data will be collected daily for up to 4 days following study initiation (until symptoms have resolved) to ascertain whether the patient had further vomiting, other sequelae of the acute gastroenteritis or required further medical care for the gastroenteritis. Data may be collected by entry by the patient or a caregiver into a web-based system or on paper, or by telephone contact daily from a study staff member. If during the follow-up period, symptoms progress or worsen or new symptoms develop, the patient may be asked to return for further evaluation. If by day 4 after discharge (i.e., the day after the last dose of study medication), the patient still notes gastroenteritis symptoms, he or she will be instructed to return for further evaluation.

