#### 4.6 Discontinuation of Treatment

Patients may take study medication daily for up to 4 days (day 1 medication is the one or two tablets administered in the emergency department).

- If a patient vomits or otherwise receives rescue medication in the emergency department, he or she is not to receive additional study medication, even if nausea and/or vomiting is controlled with rescue medication.
- If the QTc interval at 4 hours after initial dose of study medication is >500 msec, study medication is to be discontinued.
- Patients experiencing recurrent nausea or vomiting after discharge from the emergency department and initial discontinuation of study medication due to resolution of symptoms may opt to resume study medication.

If a patient experiences an adverse event, regardless of relationship to study medication, which, in the investigator's opinion endangers or makes it difficult to evaluate the patient, the investigator may elect to have the patient stop study medication.

If once on study, a patient requires a medication which may prolong the QTc interval, he or she should not receive further study medication. However, evaluation of the patient should continue per protocol.

Patients may elect to discontinue treatment at any time.

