## **8. Study Medications**

Study medication, either RHB-102 or matching placebo, will be provided by the sponsor in kits of 5, labeled with a randomization code and required drug information.

Study medication is to be stored at 15-30°C.

Each RHB-102 tablet contains a total of 24 mg of ondansetron. Matching placebo containing no active drug will also be provided.

On randomization, the appropriate bottle of study medication will be provided by ED pharmacist. The investigator or a designate will administer the first dose of study medication under observation.

If the patient vomits within 15 minutes, regardless of whether pill fragments are seen, a second dose of study medication will be administered by the investigator or a designate. If the patient experiences no vomiting in the ED after administration of the first dose of study medication, the second tablet will be retained for audit purposes. Patients who have not failed therapy before ED discharge will take the bottle containing the remaining 3 tablets home on discharge.

After each patient completes the study, he or she will send any remaining study medication back to the investigator in a prepaid, addressed mailer to be provided.

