3.1. Study Design

Patients presenting to the emergency department who fulfill entry criteria will be asked to participate. A screening log will be kept listing all patients considered with reasons for patients not entering the study. Any patient whose information is reviewed in consideration for the study, even if not actually approached, is to be included in the screening log. The screening log will differentiate between those who are prescreened, i.e., who are reviewed but never progress to request for consent, from those who are screened, i.e., who are approached for consent, whether or not they actually sign consent or eventually participate in the study. Qualifying patients, once they have signed consent, will be stratified by age (\geq vs <age 18) and randomized 60:40 to RHB-102 or matching placebo. All patients will undergo laboratory testing and ECG, as specified below, once they have signed consent. Of the blood and urine tests, only results of the pregnancy test (for women of childbearing potential) and a finger stick blood glucose (for patients with type 2 diabetes mellitus controlled by diet or oral medications) are required prior to treatment. The pretreatment ECG results are available immediately and are to be used to qualify patients.

Patients will be started on oral fluids \geq 30 minutes after taking study medication (second dose for patients who receive 2 doses in ED) if they have not vomited during that period. Intravenous hydration should not be administered unless the patient has vomited or is clearly unable, after a reasonable period of time has elapsed since administration of study medication, to tolerate oral fluids.

At 4 ± 0.25 hours after initial dosing, all patients are to have a repeat 12-lead ECG. Once stable, but not less than 4 hours after initial dosing, patients may be discharged from the emergency department. On discharge, patients who are not treatment failures will be given an additional 3 doses of study medication to take at 24-hour intervals if nausea persists. Patients will be contacted daily for 4 days after discharge to determine their condition. Those patients who have persistent, worsening or recurrent nausea and/or vomiting during the follow-up period may be asked to come in for follow-up assessment by study personnel.

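### Protocol and SAP contradict each other on further study drug after IV hydration only, after vomiting before 30 minutes, and after renewed vomiting in redosed patients

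*Protocol*

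**What the plan says.** Several places state who receives study drug beyond the ED dose.

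- Protocol Synopsis, Methodology: "On discharge, patients will be given 3 additional doses of study medication to take once daily if necessary". Protocol 4.1: "On discharge, patients will be given an additional 3 doses of study medication to take at 24-hour intervals if nausea persists". Neither sentence names an exclusion for vomiting, rescue or IV hydration.
- Protocol 4.5 supplies three doses to "On discharge, patients who have not had further vomiting and have not required rescue medication in the emergency department", and then tells patients to take them for nausea or for any vomiting.
- Protocol 4.6: "If a patient vomits or otherwise receives rescue medication in the emergency department, he or she is not to receive additional study medication".
- Protocol 8: "Patients who have not failed therapy before ED discharge will take the bottle containing the remaining 3 tablets home on discharge". SAP 3.1: "On discharge, patients who are not treatment failures will be given an additional 3 doses of study medication".
- Protocol 4.2: after vomiting within 15 minutes, "a second dose of study medication will be administered by the investigator or a designate". Then: "If a patient vomits again, regardless of how long after the second dose of study medication, no further study medication will be administered". The synopsis carries the same stop. The end of 4.2 lets admitted patients continue if they have neither vomited nor had another antiemetic; IV hydration is not mentioned.

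Protocol 4.4 and 5.2.2 define treatment failure as vomiting at or after 30 minutes from the first dose, rescue antiemetic, or parenteral hydration. Protocol 5.2.3 gives diary cards to treatment successes, described there as patients without vomiting, rescue or parenteral hydration in the ED. It sets no 30-minute limit on the vomiting.

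**The concern.** Some sections decide further supply by treatment-failure status and others by named ED events. The two criteria do not select the same patients: IV hydration is a failure but is not a named event in 4.5 or 4.6, and vomiting before 30 minutes is an event under 4.6 but not a failure. Two sites following different sections would treat the same patient differently, and both could claim compliance.

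Two things are at stake. Exposure to study drug after the ED would vary with site practice. In addition, SAP 6.5 lists doses of study medication not given per protocol as a significant deviation, and that label cannot be applied consistently while the rule is contradictory. Some follow-up outcomes would then mix patients with and without access to drug.

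**Working it through.** No figure in the plan is disputed, so the check applies each rule to each ED event.

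| ED event | Synopsis, 4.1 | 4.5 | 4.6 | Section 8, SAP 3.1 |
|---|---|---|---|---|
| IV hydration only | doses | doses | not barred | no doses |
| Vomiting before 30 min only | doses | unclear | barred | doses |
| Rescue, or vomiting at or after 30 min | doses | no doses | barred | no doses |

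**Group 1, IV hydration only.** 4.5 and 4.6 act only on vomiting and rescue, so the patient keeps access. Section 8 and SAP 3.1 act on failure, so the patient loses it. The admitted-patient rule in 4.2 sides with 4.5.

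**Group 2, vomiting only before 30 minutes.** This is not failure, so section 8 and SAP 3.1 supply tablets. 4.6 has no time limit and bars them. In 4.5 the word *further* has no stated starting point. The diary sentence in 5.2.3 would also exclude this patient, who is still at risk for both the 24-hour and 4-day endpoints. The diary pages in note c of the Study Assessments table and the daily contact later in 5.2.3 soften this but are not reconciled with it.

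**Group 3, redosed, first vomits again after discharge.** 4.2 stops study drug however long after the second dose the vomiting occurs. 4.5 says to take it for any vomiting. The last bullet of 4.6 lets patients resume for recurrent symptoms and makes no exception for redosed patients.

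**Rescue, or vomiting at or after 30 minutes.** 4.5, 4.6, section 8 and SAP 3.1 all withhold drug. Only the synopsis and 4.1 leave the exclusion out.

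**Effect on endpoints.** 4-day success uses the primary definition over a longer window (Protocol 2.2). A patient who fails in the ED is already a 4-day failure, whatever is dispensed. The composite is open only for patients who leave the ED without having failed (groups 2 and 3). In group 3 the vomiting that triggers the conflict is itself a composite failure event if it falls within the 4 days, so from then on only exposure, later components and return to the ED can differ. Those outcomes can also differ for ED failures. Take-home doses come at 24-hour intervals (4.1), so they have little room to act on the 24-hour primary endpoint.

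**Size.** Inputs from Protocol 7.1: failure 20% and 40%, arms 192 and 128. These reproduce the planned size: pooled two-proportion formula, two-sided 0.01, 90% power, ratio 1.5, gives 127 + 191 = 318 against the stated 320.

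- Expected 24-hour failures: 0.20 × 192 + 0.40 × 128 = 38.4 + 51.2 = 89.6, and 89.6 / 320 = 28%. This includes failures after discharge, so it is a ceiling on ED failures. If 25% to 100% occur in the ED (assumption), that is 22 to 90 patients, and the documents do not say how many had IV hydration only.
- Early vomiters: the documents give no rate. If 2% to 10% of the RHB-102 arm vomit only before 30 minutes (assumption; 0.02 × 192 = 3.8 to 0.10 × 192 = 19.2 patients) and access to drug changes their 4-day success by 10 to 30 points (assumption), the arm's rate moves by 0.02 × 10 = 0.2 to 0.10 × 30 = 3.0 points. That compares all patients supplied with none supplied; a mix of site practices would move it less.

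**The case against.** The strongest defence is that the synopsis and 4.1 are summaries and that the specific sections supply the missing condition. For rescue and for vomiting at or after 30 minutes this succeeds: four sections agree, and the single follow-up call for failures in 5.2.3 fits patients who go home without drug. It does not help groups 1 to 3, where the specific sections themselves conflict.

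A reader might infer that 4.6 forbids the redose in 4.2. The opening of 4.6 allows one or two tablets in the ED, so that is not shown. The 4.6 bullet can also be read as vomiting that leads to rescue, which 4.2 permits only from 30 minutes. On that reading group 2 would disappear, but the text does not say so, and the diary sentence in 5.2.3 and the admitted-patient rule in 4.2 also refer to vomiting without a time limit. For group 3, the stop in 4.2 might be meant only for dosing in the ED; again the text sets no such limit.

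A reader might also infer that doses and later events in failures go largely unrecorded. The documents do not support that. The 72 to 96 hour call asks about adverse events and further care; section 6 has all dosed patients queried on adverse events; note d of the Study Assessments table and 4.4.2 record all medication; section 8 has unused tablets returned; and 9.6 requires dispensing records by subject. What is lost is daily diary detail.

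**Conclusion.** The contradiction is real for the three groups, and it concerns drug exposure and deviation classification. It does not extend to three tempting readings. The sections do not all give different rules: several repeat one another or agree. The 4-day composite does not depend on the section followed for anyone who failed in the ED. And 28% is not the share of patients affected; it is the planned rate of all 24-hour failures, most of it outside the contested groups if IV hydration without vomiting or rescue is uncommon (assumption).

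The size of the three groups is not in the documents. Under the assumed ranges above, the effect on 4-day success in the RHB-102 arm is between 0.2 and 3.0 points, and the 24-hour primary endpoint is largely unaffected. Which rule is right is a clinical matter on which this point takes no view.

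**What to change.** Reconcile the Protocol Synopsis, 4.1, 4.2 (including the admitted-patient rule), 4.5, 4.6, 5.2.3 and 8, and SAP 3.1, into one rule chosen by the sponsor. It should state explicitly what applies after IV hydration only, after vomiting only before 30 minutes, after renewed vomiting in redosed patients, and after rescue. The diary-card sentence in 5.2.3 should use the same groups. Name in SAP 6.5 the rule against which off-protocol doses are classified.

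Tabulate actual take-home dispensing by arm and ED event type from the records required by Protocol 9.6 and the returned tablets. The Supplemental SAP (section 3) dates unblinding to June 3, 2017, so new wording cannot change conduct in this trial. The classification rule, labelled as set after unblinding, and the tabulation remain feasible. The cost is a wording change and one table, with no new data collection.
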